5.3.1 Pocket Probing Depth (PPD)

Probing Pocket Depth (PPD) will be measured by recording the distance from the gingival margin to the bottom of the probable pocket at 6 sites (mesiofacial, facial, distofacial, distolingual, lingual, mesiolingual) on the teeth in the contralateral quadrants.

Assessment will be done at screening/baseline visit and from the 3-month to the last follow-up visit.

5.3.2 Gingival Margin (GM)

The Gingival Margin (GM) measurements will be performed simultaneously with the PPD measurements. GM will be measured by recording the distance from the Cemento-Enamel Junction (CEJ) to the margin of the gingiva at 6 sites (mesiofacial, facial, distofacial, distolingual, lingual, mesiolingual) on the teeth in the contralateral quadrants.

In periodontal sites with a visible CEJ (see Figure 2), the distance from the CEJ to the margin of the gingiva will be measured as noted in the diagram below.

In periodontal sites with no visible CEJ (see Figure 3), the periodontal probe will be inserted into the periodontal pocket and angulated approximately 45° in order to manually detect the reference line. The depth of insertion into the periodontal pocket will be recorded as the GM.

A negative value for the GM indicates gingival recession. A positive value for the GM indicates the gingiva is covering the CEJ. A zero indicates the gingiva is at the same level as the CEJ.

Assessment will be done at screening/baseline visit and from the 3-month to the last follow-up visit

[figure not shown]

Figure 2: Measurement of the GM when the CEJ is visible.

[figure not shown]

Figure 3: Measurement of the GM when the CEJ is not visible

5.3.3 Clinical Attachment Level (CAL)

Clinical Attachment Level (CAL) measurements will be derived from the PPD and GM measurements as follows:

$$\text{CAL} = \text{PPD} - \text{GM}$$

Measurement will be calculated from the PPD and GM values taken at screening/baseline visit and from the 3-month to the last follow-up visit.

5.3.4 Bleeding on Probing (BoP)

Bleeding on probing (BoP) will be measured on the teeth in the contralateral quadrants. The presence of bleeding will be documented as a "yes" or "no" response on 6 sites (mesiofacial, facial, distofacial, distolingual, lingual, mesiolingual).

Assessment will be done at screening/baseline visit and from the 3-month to the last follow-up visit

5.3.5 Full Mouth Plaque Score (FMPS)

The Full Mouth Plaque Score (FMPS) according to O'Leary *et al* should be documented as an indicator for the oral hygiene on each single tooth of the mouth mesial, distal, facial, and lingual.¹² Disclosing agents should not be used to assess plaque.

The FMPS will be assessed with the following formula:

$$\frac{\text{\# of tooth surfaces with plaque}}{\text{total number of tooth surfaces}} \times 100 = \text{FMPS}$$

Assessment will be done at Visit 1, Visit 3 and at the 12-month follow-up visit.

5.3.6 Pain Scale

Postsurgical pain will be measured on a Visual Analog Scale (VAS) (Appendix 4) by asking the patient to assess their pain at three time points after treatment with minimally invasive SRP and Emdogain® application. The three time points will be 1-2 days, 1 week, and 2 weeks after surgery.

Subjects will be given a paper Case Report Form (CRF) to bring home with them and mark their responses on the VAS. The subject will mark a 100 mm scale with a vertical line directly on the CRF. The subject will then return the form to the clinic and a

measurement will be made from the left of the scale to the point of the first marking from the subject to determine the value in mm.

5.3.7 Root Dentin Hypersensitivity

Presence of root dentin hypersensitivity is examined by isolating the neighboring teeth and using a conventional air blast for three seconds on the study tooth. The root dentin hypersensitivity is recorded as "none" (no reaction from the subject), "mild" (sensible with no pain), "moderate" (sensible with slight pain), or "severe" (sensible with pain that persists for a while). Assessment will be done at Visit 2 – Minimally Invasive Scaling and Root Planing and Emdogain® First Application (SURGERY) and from the 3-month to the last follow-up visit.

5.3.8 Radiographs

Peri-apical radiographs, panoramic radiograph, or Cone Beam Computed Tomography (CBCT) of the teeth in the contralateral quadrants will be taken according to the standard practices at the clinic. Ideally images should be taken at screening/baseline visit and at the 12-month visit.

5.3.9 Intra-oral Photographs

Intra-oral photographs will be taken at each study visit to document the initial appearance of the soft tissue and the subsequent healing of the soft tissue after the study treatment. The camera alignment should be perpendicular to the labial surface of the tooth being photographed. Photographs should document all of the treated teeth. A minimum of 5 mm of the marginal soft tissue should be present in the photograph.

Three photographs are required at each visit, including one standard full mouth, and two of the right and left teeth in occlusion. If Visit 1 and Visit 2 are combined, a set of photographs should be taken pre and post-surgery.

Photographs will be labeled for easy identification of the subject and study visit.

5.4 Protocol Related Procedures

5.4.1 Point of Enrollment

The point of enrollment in this study is defined as the moment when the subject is randomized and the investigational device Emdogain® is applied at the study site, during the surgery taking place at Visit 2.

Patients enrolled in the study will be documented in the Patient and Enrollment Log.

5.4.2 Withdrawal Criteria and Procedures

Any subject may withdraw from the study at any time without prejudice and will be offered an alternative treatment for his/her dental condition. Subjects will be advised of the need for the prescribed follow-up visits for their ongoing care, well-being, and collection of any safety data.

- The Investigator may withdraw any subject from the study in the case of:
- Non-compliance with the protocol
- Failure to attend the follow-up visits
- Serious adverse event or adverse event, in the opinion of the Investigator, which prevents the subject's further participation in the study.

The subject withdrawal will be documented on a study termination form and must include the reason for the subject withdrawal. All efforts will be made to capture the primary study endpoint for each subject prior to withdrawal.

If the subject signed consent, but did not meet the inclusion/exclusion criteria, then the subject will be considered a screen failure. This will be documented on the study termination form.

If at any time a subject requires surgery during the course of the study in the region of the mouth being evaluated in the study, then the subject should be withdrawn from the study.

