8.2.5 Missing Data

Every effort will be made to minimize the amount of missing data. If subjects drop out of the study prior to completing their primary endpoint assessment, every effort will be made to measure their primary endpoint immediately prior to discontinuation if possible.

Techniques for handling missing data and the presence of outliers will be provided in the Statistical Analysis Plan.

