8.3.1 Primary Analysis of Primary Endpoint

Change in Clinical Attachment Level (CAL) between the surgery and 12 months post-surgery will be measured as the primary endpoint.

Statistics of the primary endpoint will present the seven-point scales (mean, standard deviation, minimum, 25% percentile, median, 75% percentile and maximum) of the change in CAL on the site of interest for each treatment group.

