11.4.1 Study Discontinuation

The study Center will be closed and the study terminated under the following circumstances:

- The Center is not recruiting a sufficient number of subjects or is unlikely to recruit a sufficient number of subjects
- The Center does not respond to study management requests
- Repeated protocol violations have been discovered that affect the integrity of the study or the study data.

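### Section 5.4.2 allows withdrawal for undefined non-compliance or missed visits, with no masking described and no provision to obtain those subjects' 12-month CAL

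*Combined protocol and SAP*

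**What the plan says.** Section 5.4.2: "The Investigator may withdraw any subject from the study in the case of" any of three reasons. These are "Non-compliance with the protocol", "Failure to attend the follow-up visits", and "Serious adverse event or adverse event, in the opinion of the Investigator, which prevents the subject's further participation in the study". The first two have no definition, count or threshold. The section also asks for the reason to be recorded and for the primary endpoint to be captured before the subject leaves. Section 8.2.5 repeats the second request: "every effort will be made to measure their primary endpoint immediately prior to discontinuation if possible". The endpoint itself is fixed in section 8.3.1: "Change in Clinical Attachment Level (CAL) between the surgery and 12 months post-surgery will be measured as the primary endpoint".

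Other parts of the protocol that bear on this:

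- **Treatment:** the second and last Emdogain application is at Visit 3 (5.2.3, 6.4). Visits 4 to 8 hold prophylaxis or maintenance and measurements (6.5 to 6.9).
- **Knowledge of allocation and results:** the investigator or a designee opens the envelope (5.2.1), and CAL is derived from month 3 onward (5.3.3). No masking is described.
- **Replacement and analysis set:** enrolled subjects are not replaced (5.4.4). By default, summaries use subjects with data (8.2).
- **Deviations:** they are logged (5.4.5) and summarised by type and centre (8.2.3).
- **Centres:** section 11.4.1 says "The study Center will be closed and the study terminated under the following circumstances", and the first circumstance is "The Center is not recruiting a sufficient number of subjects or is unlikely to recruit a sufficient number of subjects".

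**The concern.** After Visit 3 there is no device exposure left to stop. Withdrawal for a missed visit or a lapse in compliance then mainly ends data collection. A subject who misses months 6 and 9 could still give a month-12 CAL, yet may have been withdrawn by then. The exit measurement does not replace it, because a CAL taken at month 4 or 7 is a different quantity from change to month 12.

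Two things are at stake. The first is avoidable loss of paired observations from a sample of 50. The second is possible selection: the person applying an undefined criterion may know which quadrant is which and how each is doing. The protocol has no safeguard against that influencing who is judged non-compliant.

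**Working it through.** **The plan's own figure.** Section 8.1 gives 50 subjects with dropout of up to 15%. Then 50 × 0.15 = 7.5 lost and 50 × 0.85 = 42.5 left; in reverse, 42 / 0.85 = 49.4, which rounds up to 50. The dropout arithmetic is consistent. The 50 itself cannot be derived, because the protocol gives no alpha, power, effect size or SD.

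**Loss unrelated to the within-subject difference.** The standard error is proportional to 1/√n.

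- With 42 subjects left: √(50/42) = 1.091, about +9%.
- The 95% CI half-width is t(0.975, n−1) × SD/√n. For assumed SDs of the within-subject difference of 0.5, 1.0 and 1.5 mm it is 0.14, 0.28 and 0.43 mm at n = 50, and 0.16, 0.31 and 0.47 mm at n = 42.
- There is no bias. Each withdrawal removes both quadrants, so the two groups stay the same size.

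**Loss related to the within-subject difference.** Let the mean test-minus-control CAL gain over all 50 be 0.3 mm. This is assumed; it is the smallest whole-group split-mouth difference in the Emdogain IFU table (Appendix 1), whose other whole-group split-mouth rows give 0.5 to 0.6 mm. If k subjects averaging m mm are removed, the observed mean is (50 × 0.3 − k × m)/(50 − k).

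| k removed | m = 0.3 mm | m = 0 mm | m = −1.0 mm |
|---|---|---|---|
| 2 | 0.300 | 15/48 = 0.313 | 17/48 = 0.354 |
| 3 | 0.300 | 15/47 = 0.319 | 18/47 = 0.383 |
| 5 | 0.300 | 15/45 = 0.333 | 20/45 = 0.444 |

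For k = 5 the shift is 0, 0.03 or 0.14 mm. The value of m drives the result, and the documents give none.

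**Upper bound.** The case simulated was no true effect, with the lowest within-subject differences always the ones removed (20,000 runs, normal differences, two-sided 5% paired t-test). Removing 1, 3, 5 or 7 of 50 gave rejection rates of about 7%, 17%, 33% and 51%. Random removal stayed at about 5%. Perfect selection is not a realistic scenario; it only bounds the problem.

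**Centre closure.** If one of four equal centres were lost (assumed; 50/4 = 12.5), 37 or 38 subjects remain and the standard error rises by √(50/38) = 1.147 to √(50/37) = 1.162, or 15 to 16%. This is loss of completeness only.

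**The case against.** Several objections stand in part.

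- **The rule is permissive.** Section 5.4.2 says the investigator may withdraw, and section 5.4.5 lets a deviation be logged with the subject kept in. That is right, so a subject who lapses or does not receive the second application need not be withdrawn. But nothing says when retention applies, so the choice stays open and undefined.
- **The rules do not simply discard data.** A reader might infer that they do. The documents do not support this: an early CAL is sought, protocol care continues at Visits 4 to 8, and the grounds also apply before Visit 3, while treatment is still due.
- **Missed visits are subject-level behaviour.** They need not relate to the difference between quadrants. This also stands. The documents show that selective removal is possible, not that it happens.
- **Centre closure is a different matter.** It depends on recruitment, not on CAL, so it cannot be read as selection on results. Loss of follow-up in treated subjects is only an inference from the word terminated; section 11.4 says patients will be advised to attend follow-up for their care.
- **Exit probing before month 3 is not a contradiction of the schedule.** An exit measurement is off schedule by nature, and section 8.2.5 asks for it only where possible.
- **The study is a descriptive pilot, and missing-data methods are left to a separate SAP.** That SAP is not in the text reviewed. It could settle how exit values are used, but it cannot recover examinations that were never done.
- **Timing.** This text is Version 5.0 of 29 March 2018, while the synopsis expects follow-up to be complete by December 2017. If those dates held, wording on conduct comes too late and only the reporting part of the fix applies.

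**Conclusion.** The point holds as a gap in the withdrawal rules. Two undefined grounds, applied where no masking is described and interim paired results are visible, can end data collection before the primary endpoint, and no provision brings those subjects back at month 12.

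The likely cost is modest: about 9% on the standard error if the full 15% allowance is used. Bias ranges from none to 0.14 mm for 5 removals under the stated assumptions, and it arises only if removal tracks the within-subject difference. It would be wrong to conclude that the results are biased, or that closing a slow centre selects on outcome. What justifies a change is that the loss is avoidable through a visit already in the schedule.

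**What to change.** - **Section 5.4.2:** state that non-compliance, a protocol deviation or a missed visit is logged under section 5.4.5 and does not by itself end data collection. Collection ends on withdrawal of consent or loss to contact; other treated subjects are invited to the Visit 8 CAL examination.
- **Sections 5.4.2 and 8.2.5:** record any early-exit CAL as a dated exit value, not as the 12-month endpoint.
- **Section 11.4.1:** state that treated subjects at a centre closed for low recruitment are still invited to complete Visit 8.
- **For the sponsor:** reconcile sections 5.4.2, 7.3, 8.2.5, 11.4 and 11.4.1 on what follows withdrawal or closure. For example, 5.4.2 speaks of follow-up visits to collect safety data, while 7.3 ends adverse event reporting at withdrawal. The adverse-event ground, the surgery rule and management of the second application are clinical matters and are left to the sponsor.
- **If follow-up is already complete:** report each withdrawal with its reason, as section 8.2.4 already plans, and with the subject's last dated paired CAL.

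The cost is wording; Visit 8 is already scheduled. The small downside is that some retained subjects will be poor compliers, which the planned deviation summary (8.2.3) will show.

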3.3 Study Treatments

The workflow consists of:

Baseline evaluation:

The initial periodontal examination is conducted at the Visit 1 and includes a complete periodontal charting, including Pocket Probing Depth (PPD), Gingival Margin (GM), Bleeding on Probing (BoP), and Full Mouth Plaque Score (FMPS). This examination will be used to determine eligibility for the study based on inclusion/exclusion criteria (Section 3.7.1 and Section 3.7.2). Also, these are the baseline data used for the statistical analysis.

Treatment:

After qualification for the study, the subject will be randomized and treated with minimally invasive Scaling and Root Planing (SRP). An initial application of Emdogain® is performed during the SRP treatment for one quadrant (test). SRP alone will be performed in the contralateral quadrant (control). In addition, PrefGel® is applied on the test quadrant only (prior to the initial application of Emdogain®).

Based on the reported literature on how long Emdogain® remains in periodontal pockets^{11,10} a second application will be carried out 2-3 weeks after the initial Emdogain® application for the test quadrant to ensure longer presence of Emdogain® in the defect. Postoperative treatment is detailed in Section 5.2.3.

Re-evaluation and Follow-Up:

At 3 months, 6 months, 9 months, and 12 months after the initial application of Emdogain®, re-evaluations will be carried out in order to identify residual pockets that are indicated for perio-surgery (PPD ≥ 5 mm). This study design, including a dual application of Emdogain®, clearly aims to differentiate this treatment workflow from the approaches that have been reported in the literature.

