3.4.2 Secondary endpoints

- Change in Gingival Margin (GM)
- Change in Probing Pocket Depth (PPD)
- Change in Full Mouth Plaque Score (FMPS)
- Change in Bleeding on Probing (BoP)
- Change in root dentin hypersensitivity
- Frequency of successful probing points (PPD < 5 mm)
- Number of pockets that would normally be treated surgically that are converted to pockets that do not require surgical intervention

Additional analysis will be done at 3, 6, 9 months post-surgery:

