8.2 General Statistical Methods

A qualified statistician using validated statistical software will perform all statistical analysis according to the planned statistical testing provided in the Statistical Analysis Plan (SAP).

95% confidence intervals will be calculated based on the SAP to support the descriptive statistics, where necessary.

Unless otherwise specified, the data will be summarized for non-missing subjects in tables listing the number of subjects, and the mean, 25% percentile, median, 75% percentile minimum, maximum, standard deviation in each treatment group for continuous data (e.g., PPD, GM, CAL, FMPS and pain), or number of subjects and percentage in each treatment group for categorical data (e.g., Bleeding on Probing, Root Dentin Hypersensitivity), as appropriate. In general the denominator for the percentage calculation will be based upon the total number of subjects (N) in the study population, unless otherwise specified.

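### No analysis rule covers subjects withdrawn for surgery in the study region; under the non-missing default their failed pockets drop out of the 12-month PPD < 5 mm and conversion results

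*Combined protocol and SAP*

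**What the plan says.** - **Withdrawal.** Under section 5.4.2, if a subject needs surgery at any time "in the region of the mouth being evaluated in the study, then the subject should be withdrawn from the study". Section 3.1 makes each patient their own control, so the test and control quadrants leave together. Section 5.4.4 does not replace enrolled subjects.
- **Capture before leaving.** Section 5.4.2 adds: "All efforts will be made to capture the primary study endpoint for each subject prior to withdrawal". Section 8.2.5 repeats this: "every effort will be made to measure their primary endpoint immediately prior to discontinuation if possible". Both speak only of the primary endpoint.
- **Analysis default.** Section 8.2: "Unless otherwise specified, the data will be summarized for non-missing subjects in tables listing the number of subjects". The same section bases percentages, as a rule, on the total number of subjects.
- **Missing data.** Section 8.2.5: "Techniques for handling missing data and the presence of outliers will be provided in the Statistical Analysis Plan". The published file contains no SAP text that gives such a technique.
- **What the study looks for.** In section 3.3, from month 3 onwards, "re-evaluations will be carried out in order to identify residual pockets that are indicated for perio-surgery (PPD ≥ 5 mm"). Section 3.4.2 lists as a secondary endpoint: "Number of pockets that would normally be treated surgically that are converted to pockets that do not require surgical intervention".
- **Primary endpoint.** Section 8.3.1 describes the change in CAL from surgery to 12 months by treatment group. It does not mention withdrawn subjects.

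**The concern.** Having a pocket operated on is the opposite of having it converted to one that needs no surgery. A subject withdrawn for that reason is missing at 12 months because of the outcome. If the 12-month tables then cover only subjects with data, the conversion and PPD < 5 mm results describe the patients who did well enough to stay.

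Two effects follow. Results in both groups look better than they were. If one treatment fails more often, the comparison is also distorted, because a failure on one side removes the other side's result as well. Section 2 says that a larger trial will build on what is learned here, so an inflated control response would carry over into its planning.

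**Working it through.** **1. The plan's own figure.** Section 8.1 gives 50 subjects with up to 15% dropout. That leaves 50 × 0.85 = 42.5, so about 7 subjects may be lost. No effect size, SD, power or expected rate of surgery is stated, so the sample size itself cannot be reproduced. The 15% covers dropout from all causes and is used below as the upper illustration.

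**2. Conversion.** Section 3.7.1 requires at least 2 pockets per quadrant, so 50 subjects supply at least 100 pockets per treatment. Assume a true conversion rate of 60% and no converted pocket among the subjects withdrawn. With *w* withdrawn, the completers' rate is 60 / (100 − 2*w*).

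| Withdrawn | Counted as failures | Completers only |
|---|---|---|
| 2 | 60 / 100 = 60% | 60 / 96 = 62.5% |
| 4 | 60% | 60 / 92 = 65.2% |
| 7 | 60% | 60 / 86 = 69.8% |

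With 7 withdrawn, a true 50% reads 50 / 86 = 58.1% and a true 70% reads 70 / 86 = 81.4%. The same arithmetic applies to PPD < 5 mm counted over pockets. Section 3.4.2 names a count without a denominator. In this illustration a bare count stays at 60 and shows nothing of the failures.

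**3. Conversion when failures are one-sided.** Let both treatments truly convert 60%, and let 7 subjects leave because of the control quadrant only. Their test quadrants would have converted at 60%.
- Test: (60 − 7 × 2 × 0.6) / 86 = 51.6 / 86 = 60.0%.
- Control: 60 / 86 = 69.8%.
- Result: a false gap of 9.8 points against test.

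With a 5:2 split the figures are 54 / 86 = 62.8% and 57.6 / 86 = 67.0%, a gap of 4.2 points.

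**4. CAL, if pre-withdrawal values are not used.** The inputs are assumptions:
- Mean gains of 2.1 mm (test) and 1.5 mm (control), from an 8-month split-mouth row with 34 patients in the Appendix 1 results table.
- SD of the within-patient difference 0.6 × √34 / 2.733 = 1.28 mm, the largest compatible with that row's p < 0.01 if a paired t-test was used.
- Correlation between quadrants ρ of 0.3 to 0.5. The quadrant SD is 1.28 / √(2(1 − ρ)), i.e. 1.08 to 1.28 mm.

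Gains were simulated as bivariate normal for 2,000,000 patients. Those with the lowest worse-quadrant gain were removed with both quadrants. Perfect selection uses the true gain. Noisy selection first adds error with the quadrant's own SD.

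| Withdrawn | Selection | Control gain (true 1.50 mm) | Difference (true 0.60 mm) |
|---|---|---|---|
| 10% | perfect | 1.69–1.73 | 0.52–0.54 |
| 10% | noisy | 1.63–1.66 | 0.56–0.57 |
| 15% | perfect | 1.76–1.82 | 0.50–0.52 |
| 15% | noisy | 1.68–1.73 | 0.55–0.56 |

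A second simulation used a control gain of 1.7 mm, quadrant SD 0.8 to 1.5 mm, correlation 0.3 to 0.6 and perfect selection. When the true difference was 0 it stayed 0, although both group means rose. With 5% withdrawn the control mean rose by about 0.06 to 0.15 mm, and a true difference of 0.3 or 0.6 mm fell by only 0.02 to 0.06 mm.

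**5. How often it could happen.** Qualifying pockets start at 5 to 8 mm, so each already meets the surgical threshold in section 3.3, and a subject has at least four. If pockets behaved independently and 90% succeeded, 1 − 0.9⁴ = 34% of subjects would keep a pocket of 5 mm or more. How many of those would require surgery in the sense of section 5.4.2 is not stated.

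**The case against.** The strongest reply is that the plan leaves the matter open and does not order these subjects to be excluded. Much of that stands.

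- Both passages on capture before withdrawal cover CAL. Since CAL = PPD − GM (section 5.3.3), the pocket depth comes with it. The data may therefore exist; what is missing is a rule for using them. The effort is also only made if possible.
- The non-missing default applies unless otherwise specified, and missing-data methods are deferred to the SAP. A reader might infer that exclusion from every 12-month result is settled. The documents do not support that; they support a default with nothing stated to override it.
- The total-N denominator sits awkwardly with completers-only summaries. However, it counts subjects, while conversion counts pockets. For bleeding on probing it could even make a withdrawn subject look like one who did not bleed.
- The 3-month analysis (section 8.3.3) includes these subjects until they leave, and section 8.2.4 reports withdrawal reasons. The loss would be visible, but the 12-month estimates would not be corrected.
- Section 3.3 speaks of pockets indicated for surgery and section 5.4.2 of subjects who require it, without limiting this to periodontal surgery. A reader might infer that every residual pocket of 5 mm or more leads to withdrawal, or that 20% to 30% of subjects would leave. Neither is in the documents.
- A reader might also infer that the bias favours the device. It does not as such: both quadrants leave together, and the difference moves against whichever treatment fails less often.
- This is a pilot with descriptive summaries, and conversion is one of seven secondary endpoints. That limits the consequence without removing it.

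**Conclusion.** The point holds as a missing rule for an outcome-driven withdrawal. Followed as written, the stated defaults take failed pockets out of the 12-month conversion and PPD < 5 mm results, and the use of pre-withdrawal CAL is undefined.

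The effect is largest for conversion: about 5 points with 4 of 50 withdrawn and 10 points with 7 of 50, assuming a true 60% and no converted pocket among those withdrawn. For CAL, 15% withdrawn would raise the control gain by about 0.2 to 0.3 mm and shrink a 0.60 mm difference by 0.04 to 0.10 mm. That estimate rests on gains borrowed from surgically treated intrabony defects at 8 months, assumed correlations, and all 15% being such withdrawals. Using the pre-withdrawal CAL would reduce it. The actual withdrawal rate cannot be determined from the documents.

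**What to change.** The changes concern analysis and data collection only; the decision to operate is unchanged.

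1. In section 8.3, name surgery in the study region as an intercurrent event.
2. Count each operated pocket as not converted and not PPD < 5 mm at 12 months, with all treated study pockets as the denominator.
3. Include in the 12-month summary the CAL, PPD and GM measured before surgery, which sections 5.4.2 and 8.2.5 already seek in effect. Add a completers-only sensitivity analysis.
4. Report the numbers of subjects and pockets operated on, by quadrant.
5. Word section 5.4.2 so that, where the subject agrees, data on the unoperated quadrant continue to be collected at the visits already scheduled.
6. Reconcile sections 3.3 and 5.4.2 by stating how a pocket indicated for surgery relates to a subject who requires it.

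A mixed model over the 3-, 6-, 9- and 12-month data is optional. Items 1 to 4 and 6 cost wording in the protocol and SAP. Item 5 adds follow-up of a few more subjects.
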